To assess the effect of the new menu plan, data on food waste and consumption will be collected in each intervention school four weeks before (baseline) as well as during the four-week intervention with a 2-week break in between measurement periods. A tool for measuring food waste in school restaurants developed by the National Food Agency in Sweden will be used. The tool requires weighting (using school kitchen scales) of all kitchen waste (both preparation waste and cooking waste); all food prepared in the kitchen; the share of the prepared food that is not eaten and has to be thrown away (serving waste); the share that can be saved; and plate waste. The number of plates used daily by the pupils in the school restaurant will also be recorded. These measurements will be made daily by the personnel in the school kitchens during the baseline as well as during the intervention period. Based on these measurements, the total food consumption (kg) will be calculated as the total amount of food prepared in the kitchen (kg) minus the total amount of prepared food that is not eaten and has to be thrown away (overall waste in kg), the total amount of plate waste (kg), and the total amount of food that could be saved (kg). Plate waste per pupil (g) will be calculated for each day by dividing the total amount of plate waste by the total number of plates used. Similarly, the consumption per pupil (g) will be calculated for each day by dividing the total consumption by the total number of plates used.

Data on school meal satisfaction will be collected at each intervention school through an online questionnaire at baseline and during the last week of the intervention period. Pupils in grades 5 and 8 answer the questionnaire containing ten questions related to the school lunch. Five of the ten multiple-choice questions specifically cover their general (i.e. not for that specific day of week) sense of satisfaction with the school lunch. The questions include how often they consider that the school lunch tastes good, how many days per week that they tend to eat from the school lunch, how often they usually feel full after having eaten lunch, and how often they tend to throw away food in the school restaurant. They are also asked to provide an overall rating of the school lunch.

Qualitative study

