Six focus group discussions (FGD) with pupils in grades 5 and 8 and three FGDs with meal staff will be conducted to explore their experiences with the intervention as well as the barriers and facilitators to scaling up.

Statistical analysis plan

In order to compare food waste and consumption between the two periods (baseline and intervention), interrupted time-series (ITS) analysis will be used [7]. ITS analysis will be implemented at school level to assess the difference between the two periods daily in the number of pupils consuming lunch (n), kitchen waste (kg), prepared food (kg), serving waste (kg), total plate waste (kg), plate waste per pupil (g), total consumption (kg), and consumption per pupil (g).

The ITS analysis will be based on linear regression models [7]. These models will be determined by three independent variables: (a) A time-variable, applied to adjust for a potential baseline trend; (b) A variable indicating whether the data point represented the baseline or intervention period to assess the level (mean) change resulting from the intervention; and c) an interaction term between (a) and (b) specifying

the slope change resulting from the intervention. Assumptions of normality, homoscedasticity, as well as absence of autocorrelation and partial autocorrelation will be assessed.

The effect of the new menu plan on the five questions related to school meal satisfaction will be explored with Pearson's chi-squared tests (χ^2) within each intervention school.

The software R (version 3.6.1) [8] will be used for statistical analysis.

Qualitative content analysis [9] will be used to analyze the FGDs.

References

3. UN General Assembly (2015) Transforming our world : the 2030 Agenda for Sustainable Development. UN General Assembly
4. (2015) Paris Agreement. UNFCCC

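### The daily ITS models omit day of the week, so a weekday pattern would miscalibrate the level change in a direction that depends on the pattern

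*Combined protocol and SAP*

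**What the plan says.** The Outcomes section says of the waste and consumption data: "These measurements will be made daily by the personnel in the school kitchens during the baseline as well as during the intervention period". Collection runs for four weeks at baseline and again "during the four-week intervention with a 2-week break in between measurement periods".

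The Statistical analysis plan section states "ITS analysis will be implemented at school level to assess the difference between the two periods daily", and lists eight outcomes. On the model it says "The ITS analysis will be based on linear regression models" and "These models will be determined by three independent variables". The first is "A time-variable, applied to adjust for a potential baseline trend"; the others are a period indicator for the level change and the product of the two for the slope change. On diagnostics it says "Assumptions of normality, homoscedasticity, as well as absence of autocorrelation and partial autocorrelation will be assessed". It names no action if a check fails.

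Day of the week appears nowhere in the model. Its only mention is in the Outcomes section, where the satisfaction questions are said not to concern a particular day.

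**The concern.** School-day data come in blocks of five, and attendance or dishes may differ by weekday. If they do, the three-variable model is affected in two ways.

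- **Residual variance.** The weekday pattern is counted as random error, so the reported standard error exceeds the true sampling spread.
- **Trend.** A pattern that is higher at one end of the week tilts the fitted line within each period. The level change projects the baseline line across the two-week break, so even a small tilt carries into it.

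The Introduction's hypothesis is that the optimized menu does no harm to waste, acceptance or cost. An inflated standard error makes an absence of significant change easier to find. A biased level change could hide a real change or create a false one. Each school is analysed as its own short series, so pooling does not recover the lost precision.

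**Working it through.** The plan states no SD, effect size or power, so it has no figure of its own to reproduce.

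**Inputs.** From the documents: daily values, 4 + 4 weeks, a 2-week break, and a three-variable linear regression per school. Assumed: five school days a week without closures (20 + 20 = 40 points, 40 - 4 = 36 residual df), time counted in school days (0-19 and 30-49), level change read at the first intervention day, independent errors, total daily variance 1, and the same weekday pattern in both periods. The weekday share R of daily variance is not given; 20% is the main case and 0-40% the range.

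**Step 1: precision of the level change.** The model fits a separate line in each period. Within a period the mean day is 9.5 and Sxx = 20 × (20² - 1)/12 = 665.
- Baseline line projected to day 30: 1/20 + 20.5²/665 = 0.050 + 0.632 = 0.682.
- Intervention line at its first day: 1/20 + 9.5²/665 = 0.050 + 0.136 = 0.186.
- Sum 0.868; square root 0.931.

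**Step 2: midweek peak, R = 0.2.**
- True SE = 0.931 × √0.8 = 0.83.
- The pattern is uncorrelated with the three variables, so all of it stays in the residual: 0.8 + 0.2 × 40/36 = 1.022.
- Reported SE = 0.931 × √1.022 = 0.94.
- Simulation gives 0.94 against 0.84, a ratio of 1.12. At R = 0.1 it gives 0.93 against 0.89, and at R = 0.4, 0.95 against 0.72.

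**Step 3: bias from asymmetric patterns, R = 0.2.** Number the weekdays k = -2 to 2, with effects m(k). Each fitted slope picks up b = 4 Σ k·m(k) / 665. The level change then moves by -9.5b - 20.5b = -30b.
- Monday-to-Friday gradient, m(k) = √0.2 × k/√2: Σ k·m(k) = 3.162, b = 0.0190, bias = -0.57.
- Friday-only, m = √0.2 × (-0.5, -0.5, -0.5, -0.5, 2): Σ k·m(k) = 2.236, b = 0.01345, bias = -0.40.
- Any pattern symmetric around midweek: Σ k·m(k) = 0, bias 0.

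Reversing a pattern reverses the sign. Bias grows with √R, so at R = 0.4 these become 0.57 × √2 = 0.81 and 0.40 × √2 = 0.57. Both periods pick up the same b, so the slope change is unbiased when weeks are complete.

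**Step 4: simulated type I error of the level change (nominal 5%), planned model.**

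| Pattern | R = 0.2 | R = 0.4 |
|---|---|---|
| Midweek peak | 2.9% | about 1% |
| Friday-only | 4.5% | 3.8% |
| Monday-to-Friday gradient | 6.6% | 7.3% |

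With four weekday indicators the bias disappeared in every pattern tried and type I error was about 5%. The table uses school-day coding. With calendar-day coding the gradient bias at R = 0.2 is smaller, about 0.41, and no excess over 5% is claimed there.

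**Step 5: price of the indicators.** The variance of the level change rises by a factor of 1.05, and √1.05 = 1.025. With 32 instead of 36 df, intervals are 2-3% wider at R = 0. The ratio of planned to adjusted interval width is 0.97-0.98 at R = 0, 1.03-1.04 at R = 0.1 and 1.09-1.11 at R = 0.2. Break-even for the level change is at R of about 3-5%.

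**Step 6: serial correlation.** Midweek peak, R = 0.2, ordinary regression, lag-1 correlation 0.2 (assumed):
- Planned model: reported SE 0.92, true 0.99, type I error 6.6%.
- With weekday terms: reported SE 0.83, true 1.01, type I error 10.3%.

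At lag-1 correlation 0.1, type I error goes from 4.3% to 7.5%.

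**The case against.** The strongest reply is that the documents show no weekday pattern, and that the planned autocorrelation checks could reveal a five-day cycle. The first part stands: every size above is conditional, and the share may differ among the eight outcomes, for example between number of diners and plate waste per pupil. The second is weak. At a 20% share the mean lag-5 autocorrelation is about 0.13, against an approximate limit of 1.96/√40 = 0.31, so a moderate pattern would usually pass unnoticed.

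Two further objections stand and limit the remedy. Weekday terms alone do not give correct standard errors under serial correlation; Step 6 shows that they can make matters worse under ordinary regression. Also, the Optimization section has a meal planner build a new menu, so a pattern driven by dishes may change between periods. With a 20% pattern shuffled between periods, shared indicators lowered the reported SE only from 0.93 to 0.91, compared with 0.94 to 0.85 for a stable pattern.

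A reader might infer that the intervals are always too wide, and that the plan therefore leans towards finding no harm. The documents do not support that. They do not describe any weekday pattern, an asymmetric one can raise type I error above 5%, and positive serial correlation can make the same intervals too narrow.

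**Conclusion.** The omission is clear from the text, and its consequence is conditional. If weekdays carry a non-trivial share of daily variance, inference on the level change is miscalibrated. For a 20% share the reported SE is about 12% too large under a midweek peak. With school-day coding, the bias is about 0.6 daily SDs under a Monday-to-Friday gradient and about 0.4 under a Friday-only pattern. These figures rest on about 40 complete school days per school, independent errors, a pattern common to both periods, and the level change read at the first intervention day. School closures would unbalance weekdays between periods and could add bias. The point is a cheap improvement, because the possible loss from adding the terms is small and the possible gain is larger. It does not show that the planned analysis is invalid.

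**What to change.** In the Statistical analysis plan section, state that each ITS model includes four day-of-week indicators (Monday as reference) in addition to the three variables, and that the residual autocorrelation and partial autocorrelation checks are run on this model. In the same place, prespecify autocorrelation-robust standard errors (for example Newey-West) or an autoregressive error model if correlation remains. With about 40 points per school either remedy is approximate, and the report should say so.

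The cost is a sentence or two in the plan and 4 of 36 residual degrees of freedom per school. No new data are needed, because the dates are known. If there is no weekday pattern, level-change intervals are about 2-3% wider. The terms handle stable patterns such as attendance; the plan should note that they do not handle dish-driven patterns that differ between the two menus.

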Study protocol with statistical analysis plan

Fostering sustainable dietary habits through optimized school meals –
OPTIMAT

Date: November 14, 2019

Introduction

Public school meals have been highlighted as a suitable setting for children to internalize sustainable dietary habits, which may persist throughout life [1, 2]. Radical changes to food production and consumption are needed to ensure the attainment of Agenda 2030 for Sustainable Development [3], and fulfillment of the Paris Agreement [4]. Planning of school meals must take many aspects into account: health promotion, environmental impact, acceptability by the consumers and affordability to those paying for the meals. Currently many schools use organic products, recycle food packaging and aim to reduce food waste, but environmental impacts like greenhouse gas emissions (GHGE) have so far not received much attention.

In Sweden, fully subsidized lunches are served daily in primary schools to all 1.3 million children aged 6 to 15 [5]. Due to their reach and scale (approximately 230 million meals/year at an annual cost of around 5.6 billion SEK), school meals have enormous potential to increase children's knowledge about health and sustainability, foster sustainable dietary habits and to enable sustainable public procurement.

This study aimed to: a) apply linear programming to develop a GHGE-reduced, nutritionally adequate, and affordable four-week lunch menu plan optimized for minimum deviation from the current food supply; and b) evaluate the climate impact of the menu, effects on food waste, food consumption, and pupils' satisfaction with school lunches. Our hypothesis is that school meals can be optimized to be nutritious and more climate friendly, without negatively affecting acceptance, food waste and cost.

Methods

Design

An interrupted time series (ITS) analysis design will be used to compare the effect of an optimized menu to the baseline menu on daily food waste and consumption at school level. For a baseline period of four weeks children in primary schools will receive a baseline menu. After a two-week break, the optimized four-week menu will be served (intervention period).

Recruitment of schools

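### The five satisfaction items are ordered in kind, but the only planned analysis, Pearson's chi-squared within each school, gives no direction, size or interval for a change in acceptance

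*Combined protocol and SAP*

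**What the plan says.** The Outcomes section describes "an online questionnaire at baseline and during the last week of the intervention period", answered by pupils in grades 5 and 8. Five multiple-choice items cover satisfaction. Three are frequency questions: "how often they consider that the school lunch tastes good", how often pupils feel full, and "how often they tend to throw away food in the school restaurant". One asks on how many days of the week they eat the lunch. For the last, "They are also asked to provide an overall rating of the school lunch". The answer options are not listed, but all five items are ordered in kind.

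The Statistical analysis plan section gives these items one quantitative analysis: "The effect of the new menu plan on the five questions related to school meal satisfaction will be explored with" Pearson's chi-squared tests, school by school. It names no effect measure, direction, interval or ordinal method for them. For waste and consumption it does name an effect: a period term "to assess the level (mean) change resulting from the intervention", together with a slope change.

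Satisfaction belongs to aim (b) in the Introduction, which continues: "satisfaction with school lunches. Our hypothesis is that school meals can be optimized to be nutritious and more climate friendly", and this is to be achieved "without negatively affecting acceptance, food waste and cost".

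**The concern.** The hypothesis on acceptance has a direction: the new menu should not make things worse. The planned test has none. Pearson's chi-squared asks only whether the two answer distributions differ in any way. It does not use the order of the categories, and it yields no estimate or interval.

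Two things are at stake. A significant result would not by itself say whether satisfaction rose or fell. A non-significant result would not show which falls remain compatible with the data, and that is what a reader needs in order to judge a claim of no negative effect.

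**Working it through.** **Inputs.** The documents state no pupil numbers, answer categories, significance level, margin or number of schools for satisfaction, so there is no planned figure to reproduce. Everything numerical below rests on assumed inputs. Odds ratios (OR) are for a more favourable answer in the intervention period than at baseline, so values below 1 mean a fall.

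**1. Direction and order.** Assume 100 pupils per round and five categories, from worst to best 8/17/30/30/15 at baseline and 14/23/30/23/10 in the intervention period. With equal group sizes the expected count is the category mean (11, 20, 30, 26.5, 12.5), so

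χ² = 2 × (3²/11 + 3²/20 + 0 + 3.5²/26.5 + 2.5²/12.5) = 1.64 + 0.90 + 0 + 0.92 + 1.00 = 4.46, df 4, p = 0.347.

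Swapping the periods or scrambling the categories leaves every term unchanged, so the result is again 4.46 and p = 0.347. A proportional-odds model on the same table gives OR 0.587 (95% CI 0.356 to 0.967) for the fall. With the periods swapped it gives the reciprocals: 1/0.587 = 1.70, with limits 1/0.967 = 1.03 and 1/0.356 = 2.81. The rank-sum p-value is 0.037.

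**2. Power for an ordered shift.** The simulation uses 6,000 replicates and a latent normal variable cut at 8/17/30/30/15%, with a two-sided 5% level and no clustering. The correlation between a pupil's two answers is 0 to 0.7. The shift is a fall of 0.3 SD (top two categories 45% to 34%, OR about 0.60).

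| Pupils per round | Chi-squared | Ordinal shift |
|---|---|---|
| 100 | 19–32% | 51–53% |
| 200 | 61–63% | 81–93% |
| 300 | 81–89% | 94–99% |

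**3. The reverse case.** If opinion splits (no mean shift, 1.5 times the spread, lowest category 8% to 17%, OR 0.98), chi-squared detects it in 62–66% of replicates at 100 per round and 94–96% at 200. The ordinal shift does so in at most 6%.

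**4. What an interval would show.** With no change and 100 per round, one school's 95% CI is typically OR 0.61 to 1.64. Baseline odds of a top-two answer are 0.45/0.55 = 0.818. Then 0.818 × 0.61 = 0.50, or 33%, and 0.818 × 1.64 = 1.34, or 57%. A fall from 45% to 33% would still be possible, and a non-significant chi-squared would not reveal that.

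**5. How far that interval can be trusted.** With no change and independent pupils, coverage is 95.2%. If the same pupils answer twice (correlation 0.5 to 0.7) but are analysed as unlinked, coverage is 99.3–99.9%, so the interval is too wide. Now assume four classes, and let pupils in one class in one round share 2%, 5% or 10% of the variance. Over correlations 0 to 0.7, coverage becomes 90–98%, 83–90% or 72–79%, so it is mostly too narrow. Chi-squared is affected too, rejecting 2–7%, 6–12% or 12–20% of the time. A pupil-level signed-rank test on linked answers that ignores class is worse, rejecting 14–19%, 24–34% or 38–47%.

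**The case against.** Five counter-arguments carry weight.

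- **Chi-squared is not a wrong test.** Step 3 shows a harm, a doubling of the lowest category, that it detects and a single shift misses. This stands, and is why the test should be kept. A reader might infer that the planned analysis is invalid, but nothing in the documents supports that. What is missing is an estimate.
- **The plan only explores these items.** It sets no significance level for them and claims no equivalence. A reader might infer that non-significance will be taken as unchanged acceptance, but the plan does not say so. Plate waste, consumption per pupil, pupil numbers at lunch and six pupil focus groups also bear on acceptance. All this limits the consequence. It does not supply a quantitative, directed answer from the pupils' own ratings.
- **Direction can be read from the cross-table.** It can, but the plan does not commit to reporting the table, and percentages without intervals do not show which falls remain possible.
- **The contrast with the time-series analysis is partial.** That analysis is also at school level and names no interval or pooled estimate. The real difference is only that it names an effect. The lack of an overall satisfaction estimate is therefore not a separate fault.
- **The illustration is model-dependent.** In the step 1 table the top-two difference is −12 points, with standard error √(0.45 × 0.55/100 + 0.33 × 0.67/100) = 0.068 and a 95% CI of about −25 to +1. The clear fall thus depends on using all five categories. By 300 per round the power gap is also only about 10 to 13 points.

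A reader might also infer that the plan wrongly ignores pairing. The documents do not say whether the same pupils answer twice or whether answers can be linked, so that is not established.

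**Conclusion.** The point holds as a minor-to-moderate omission. The items are ordered by their wording and the hypothesis on acceptance is directional, yet the only planned quantitative analysis carries neither order nor direction and gives no size or interval. By itself it cannot address whether acceptance was negatively affected. That much is a property of the statistic and needs no assumption beyond the ordered nature of the items.

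The size of the loss does rest on assumptions: five categories, 100 to 300 pupils per round, a 0.3-SD fall and no clustering. On those inputs the ordinal shift gains most at 100 to 200 pupils per round and less at 300. The figures do not show that this study is underpowered, because its pupil numbers are not stated. An ordinal interval is also not safe by default, since class clustering of the assumed size could cut its coverage to between 72% and 90%.

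**What to change.** Change the SAP wording; no new data are needed.

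1. For each item and school, report the answer distribution in both periods and a pre-specified directed ordinal change (for example a proportional-odds odds ratio) with a 95% CI. Name this in advance as the main summary. State the favourable direction per item, because the throw-away item runs opposite to the others.
2. Keep Pearson's chi-squared beside it as supporting, since a single shift can miss split opinion.
3. If class is recorded, allow for class clustering in this main interval. If not, label the interval approximate, note that clustering makes it too narrow and pupil overlap too wide, and do not present it as firmly excluding a fall.
4. State that a non-significant result is not read as unchanged acceptance.
5. State whether answers are linked. Add a paired ordinal model only if they are and class clustering is handled. A school-adjusted overall estimate is optional.

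The cost is a little more analysis and reporting, reliance on an approximate proportional-odds assumption, and two results per item. The last adds some chance findings, which is why the main summary should be named beforehand.
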